10.4.4 Relationship between AE and vaccination

Investigators should make the best interpretation of AE, and assess the possible causal relationship between vaccination and reactions (such as history of underlying diseases,

combined treatment of causation). This applies to all AEs, including severe ones and non-severe ones.

The assessment of causality will be reasonably explained in the following or more aspects of the event:

- The similar reaction to the solution was observed in the past;
- identical events of similar types solution have been reported in the literature;
- the incident occurred along with the time of the vaccination, and again after the secondary vaccination

According to definitions, all the solicited AE (that is, the local adverse event of the collection of the report) will be considered to be related to vaccination.

The causal relationship of AE should be evaluated according to the following questions, and according to your judgment, the reasonable possibility of relationship between AE and vaccination is caused by the vaccination:

- Related: there is a suspicion that a link between vaccine and the AE (do not need to be determined); the vaccine has a reasonable potential for promoting the AE.
- Unrelated: there is no suspicion that a link exists between vaccine and the AE; there are other more likely causes, and vaccination has not been suspected to promote the AE.

10.4.5 Reporting of SAEs

Any serious adverse event, including death due to any cause, which occurs during this study, whether or not related to the investigational products, must be reported immediately (within 24 hours of the investigator's knowledge of the event) by

telephone or fax to the sponsors, principle investigator, JSCDC IRB, Health Bureau of Logistics Support Department of CMC, and Hubei Medical Products Administration, at the following number:

Principal Investigator: [name], [contact], [contact]

Representative of sponsor: [name], [contact]

JSCDC IRB: [name], [contact]; [contact]

Upon receipt of information about vaccine safety from any source, the sponsor shall conduct an analysis and assessment, including severity, relevance to the study, and whether it is an expected adverse event.

For suspicious and unexpectedly serious adverse reactions that are fatal or life-threatening, the sponsor shall report to Health Bureau of Logistics Support Department of CMC and National Medical Products Administration as soon as possible, no more than 7 natural days, and update the relevant information within the following 8 days;

For information about suspicious and unanticipated serious adverse reactions that are not fatal or life-threatening, or other potential serious safety risks, the sponsor shall report to Health Bureau of Logistics Support Department of CMC and National Medical Products Administration as soon as possible after it is first known, but not more than 15 natural days.

10.4.6 Record of safety observation

Any clinically meaningful adverse event occurred after vaccination should be recorded in the diary card.

Verification and medical visits by investigator respond to adverse events are required,

such as investigation of medical history, physical examination and necessary laboratory examination (if required). Participants should receive appropriate medical treatment until the adverse event decline completed with complete records.

The record of adverse events should include the following:

- Description of adverse events
- Start and end time of adverse events
- Severity (grade)
- Relationship with vaccination
- Laboratory findings
- Treatment measures
- Outcome

If there are allergies, SAE, or a grade 3 adverse events or above happening in safety observation period, medical treatment should be provided until symptoms disappeared or stabilization of symptoms.

10.4.7 Medical treatment of AE

If the participants report injection-site or systemic adverse reactions or events or serious adverse events, investigators should provide appropriate treatment or medical consultation to reduce or remove suffering. The medical treatment of green channel could be started if it is necessary. The medical procedures and outcome should be exactly recorded.

10.5 Biological sample collection and examination

10.5.1 Detection of ELISA Antibody against SARS-CoV-2 's S protein

10.5.1.1 Detection time point

Specific S protein antibody titers in serum against SARS-CoV-2 will be detected on day 0, day 14, day 28, month 3 and month 6 after immunization.

10.5.1.2 Blood sample processing and detection methods

The SOP for serum isolation is shown in Appendix 1, and the SOPs for storage and transportation by serum are shown in Appendix 2. The SOP for detecting SARS-CoV-2 antibody by ELISA is in Appendix 3.

10.5.1.3 Evaluation content

The level of specific S protein antibody in serum against SARS-CoV-2 on day 28 post-vaccination will be used as the primary evaluation time point for immunogenicity. The differences of antibody levels among different groups and the changes of antibodies at various time points pre-vaccination and the post-vaccination will be compared.

10.5.2 Detection of neutralizing antibody against SARS-CoV-2

10.5.2.1 Detection time point

Serum neutralizing antibody titers against SARS-CoV-2 will be determined at day 0, day 14, day 28 and month 6 after immunization.

10.5.2.2 Blood sample processing and detection methods

The SOP for isolation of serum is shown in Appendix 1, and the details of SOP preserved and transported by serum are shown in Appendix 2.

The SOP of detecting SARS-CoV-2 antibody by pseudo virus neutralization test is detailed in Appendix 3.

10.5.2.3 Evaluation content

The level of serum neutralizing antibody against SARS-CoV-2 on day 28 of vaccination will be used as the primary evaluation index of immunogenicity. The differences of

antibody levels among different groups and the changes of antibodies at various time points pre-vaccination and the post-vaccination will be compared.

10.5.3 Detection of specific CD4+ T cell and CD8+ T cell response

10.5.3.1 Detection time point

Specific CD4+ T cell and CD8+ T cell responses will be detected at day 0, day 14 (main evaluation time point), day 28 and month 6 after immunization (IL-2, IFN- γ and TNF will be secreted by S protein overlapping peptide library will be detected by intracellular cytokine staining).

10.5.3.2 Blood sample processing and detection methods

PBMC isolation and cryopreserved SOP from human peripheral blood mononuclear cells are shown in Appendix 4. For SOP detection of T cell response by intracellular cytokine staining, see Appendix 5.

10.5.3.3 Evaluation content

The positive rate of T cell reaction on day 28 of vaccination will be used as the main evaluation index of immunogenicity. The differences of antibody levels among different groups and the changes of T cell reaction positive rate at each time point pre-vaccination and the post-vaccination will be compared.

10.5.4 Detection of IFN- γ secreted by specific T cells

10.5.4.1 Detection time point

IFN- γ secreted by specific T cells will be detected at day 0, day 14 (major evaluation time point), day 28 and month 6 after immunization.

10.5.4.2 Blood sample processing and detection methods

The SOP for the isolation and cryopreservation of human peripheral blood mononuclear

cells (PBMC) is shown in appendix 4. The SOP for the detection of T cell reaction by ELISpot method is shown in appendix 6.

10.5.4.3 Evaluation content

The positive rate of T cell reaction on the 28th day of vaccination will be used as the main evaluation index of immunogenicity. The differences of antibody levels among different groups and the changes of T cell reaction positive rate at each time point pre-vaccination and the post-vaccination will be compared.

10.5.5 Detection of neutralizing antibody to recombinant replication defective human type 5 adenovirus

10.5.5.1 Detection time point

Serum neutralizing antibody titers against recombinant replication defective human type 5 adenovirus will be detected at day 0, day 14, day 28, month 3 and month 6 after immunization.

10.5.5.2 Detection methods

The SOP of neutralization antibodies against human type 5 adenovirus will be detected by cell neutralization test is shown in appendix 7.

10.5.5.3 Evaluation content

The levels of neutralizing antibodies against human type 5 adenovirus, the growth times of antibodies and the differences among groups will be compared pre-vaccination and the post-vaccination. To explore the correlation between the level of baseline neutralizing antibody against human type 5 adenovirus and S protein ELISA antibody and T cell response.

10.5.6 Surveillance and laboratory diagnosis of SARS-CoV-2 infection during

clinical trials

During the observation period of the clinical trial, the participants with fever, cough and other respiratory symptoms should immediately go to the designated hospital (Guanggu Hospital affiliated to Tongji Hospital, Tongji Medical College, Huazhong University of Science and Technology) and inform the investigators. The doctor or investigator will collect the pharyngeal swabs (or sputum) and anal swabs and to perform CT and other imaging examinations to analyze whether it is caused by SARS-CoV-2 infection. In the event of SARS-CoV-2's infection during the clinical trial, it is necessary to conduct a case investigation, and the critically ill or dead cases need to continue to conduct a special investigation of critical or dead cases, mainly to analyze whether there is an ADE phenomenon.

In addition to SARS-CoV-2 nucleic acid detection, multiple pathogens will be detected for differential diagnosis of pharyngeal swabs or sputum and anal swabs.

10.6 Data management

In this study, the electronic data collection (EDC) system is used to collect and manage the study data. The system keeps a complete modification track to ensure the authenticity, completeness and accuracy of the clinical trial data. The data management process should comply with the GCP specification to ensure the traceability of the clinical trial data.

10.6.1 Data collection, entry and reporting

10.6.2 Data collection roles and responsibilities

Data collection roles	Abbreviation	Responsibilities
Clinical research coordinator	CRC	1. Input data; 2. Answer questions;
Sub-investigator	Sub-I	1. Input data; 2. Answer questions;
Principal Investigator	PI	1. Input data; 2. Answer questions; 3. Approve and confirm (approve);
Clinical research associate	CRA	1. Source file consistency verification (verify); 2. To question; 3. Close the query;
Project manager	PM	1. Read-only;
Data manager	DM	1. To question;

		2. Close the query;
		3. Freezing / thawing data;
		4. Lock the data;
Medical coder	coder	1. Encoding;
		2. To question.

10.6.3 Design and establishment of database

The project database (eCRF) is established by the database designer, and the database is established by CDISC standard as much as possible.

After the database is established and tested, the authorized personnel of various roles, such as PI, Sub-I, CRC, PM, CRA, DM, etc., can be officially put online after training.

The data administrator writing the data management plan (DMP), DMP should be finalized before the first subject screening.

10.6.4 Data entry

The investigator or the person authorized by the investigator completes the online data entry in time after completing the visit.

The investigator need to approve and confirm the data on the eCRF in order to confirm that the data recorded in the eCRF are true. After data entry is completed, any data changes need to be explained and will be automatically recorded in the system.

10.6.5 Monitoring of data records

Auditors should conduct regular and irregular audits of data records entered into the EDC to ensure that all the input data are consistent with the original documents. If there is any inconsistency, the auditors needs to send queries to the investigators in the corresponding place in the EDC system, and the investigators need to verify the original

data and update the input until the EDC system is complete. Before locking the library, the auditors should carefully verify the original data of the subjects and the necessary signatures of the investigators.

10.6.6 Data verification

Data managers query and manage the test data according to the data verification plan (DVP).

When data is entered into the EDC system, if there is illogical data, the system will automatically check and query. These queries need investigators or authorized personnel to review and answer, when the updated data makes the logical verification not valid, queries will automatically shut down. Automatically closed queries, DM can be audited, when the problems are not solved, DM can manually add questions and continue to communicate with the study center until the problems are solved.

In addition to the automatic verification of the system, the queries checked by SAS programming or data administrator can be manually added to the EDC system when the investigators are required to clarify, verify or confirm.

Before locking the database, the data administrator needs to make sure that all the queries are cleaned up, and the investigators complete the electronic signature on the EDC system to ensure the integrity and accuracy of patient data.

10.6.7 Medical coding

Medical coders carry out medical coding for unsolicited adverse events. Adverse events will be encoded according to the MedDRA (version 21.1 or above).

During the coding process, DM can query the investigators in real time if any medical

terms cannot be coded due to improper, inaccurate or vague provision of medical terms.

The medical code needs to be reviewed before the database is locked.

10.6.8 The database lock

After completing the data lock list, according to the procedures for database lock, data managers, statistical analysts, clinical auditor representatives, and investigator representatives will sign and approve database lock. It is exported by the data administrator to the database in the specified format, and then handed over to the statisticians for statistical analysis. After the database is locked, if there is definite evidence to prove that it is necessary to unlock, the investigators and relevant personnels must sign the unlocking document.

10.6.9 External data management

Immunogenicity data is managed as external data. For data transmission requirements, please refer to "External Data Transmission Protocol". The data administrator audits and verifies the external data.

10.6.10 Archive eCRF

At the end of the trial, the eCRF of each patient is exported to PDF for electronic archiving, and the CD-ROM was stored in the Wuhan Special Service Rehabilitation Center of the Chinese People's Armed Police Force for a period of 5 years after the completion of the trial.

10.7 Statistics plan and statistical analysis

10.7.1 Statistics plan

In this study, the statistical analysis includes initial analysis and the final analysis.

10.7.1.1 Initial analysis

After the last participant complete the Visit 6 (28 days after vaccination), the research database has been entered, audited and locked, initial analysis will be done by the statistical party. The initial statistical analysis report shall first be reviewed by the DSMB and determined that the report shall be carried out in strict accordance with the initial statistical analysis plan before it can be submitted to the researcher and sponsor.

10.7.1.2 The final analysis

After the last participant complete the Visit 8 (month 6 after vaccination), all the data of serious adverse events from Visit 6 (day 28) to Visit 8 (month 6), and the data of humoral and cellular immunity will be analyzed and summarized.

10.7.2 Statistical analysis plan

The sponsor shall entrust the statistical party to undertake the task of statistical analysis and participate in the whole process from the design, implementation of the experiment to analysis and summarization, after the formulation of the test scheme has been completed and approved by the Ethics Committee, the sponsor shall be responsible for coordinating the establishment of the database and the formulation of the statistical analysis plan to determine the analytical data set and statistical methods (see "Initial Statistical Analysis Plan" and "Final Statistical Analysis Plan" for details).

10.7.3 Analyzed data sets selection

Data set for safety evaluation

All participants who received vaccination should be included in the safety evaluation.

Data that violate the scheme should not be excluded.

Data set for immunogenicity evaluation

Full analysis set (FAS) for immunogenicity analysis: FAS is based on ITT (intention to treat analysis) principle to determine the participants. All of the participants that meet the inclusion / exclusion criteria, receiving vaccination, and have at least one blood testing result after vaccination, were included in the FAS set for immunogenicity.

Per-protocol set (PPS): It is a subset of FAS. The participants in the data set were more compliant to the scheme, with no significant deviation or violation of protocol, all met the selection/exclusion criteria and completed vaccination within the vaccination time window according to the requirements of the scheme, and the participants who collected blood at day 0, day 7, day14, day 28 day, month 3 and month 6 month were included in the PPS set. This method of analysis does not include participants who violate the protocol, and confirmed as COVID-19 cases within 14 days after vaccination.

In this study, the FAS are the primary analysis set for immunogenicity evaluation, but the PPS will also be analyzed at the same time. Any difference of analysis results existed between PPS and FAS, will be discussed in the report.

10.7.4 Data statistical methods

In statistical analysis, the number of completed cases will be checked first; then the demographic and baseline characteristics of each group are going to be analyzed to examine the comparability between groups; the evaluation of vaccine effect included the determination of evaluation indicators and the comparison of effects between groups; safety evaluation included statistics of clinical adverse reactions / events.

Exclusion criteria: did not meet the selected case criteria; failed to follow up data and information after vaccination; serious lack of information and data; Participants met the withdrawal criteria but did not withdraw; Participants received the wrong vaccination or incorrect dose.

Safety analysis is mainly descriptive analysis of incidence rate of adverse reaction or adverse events. A chi-square test can be used to compare the proportion of participants with adverse reactions in different groups, Fisher's exact test will be used when it is necessary. Analysis of immunogenicity indicators on antibody levels need to do logarithmic transformation, the results of analysis should be shown in GMT, standard deviation, median, minimum and maximum values and 95% confidence intervals. Chi-square test can be used to compare categorical indicators between groups such as positive conversion rate of immune response, if it is necessary, Fisher's exact test will be used. All statistical calculations will be processed by SAS 9.4 statistical analysis system. $P \leq 0.05$ will be considered as statistically significant different (see the initial statistical analysis plan and the final statistical analysis plan for details).

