9.4 Withdraw from the study

Participants have the right to withdraw from the study at any time during the study period, and the investigator should record the reason of withdraw:

- Participants become pregnant.
- Loss of contact.
- Request to withdraw without any reason.
- Withdraw for reasons unrelated to the study, such as long-term departure,

relocation, etc., and the specific reason for withdrawal should be recorded.

- Withdrawal for reasons related to the study, such as intolerance of adverse reactions, intolerance of biological specimen collection, etc., and the specific reason for withdrawal should be recorded. If a participant withdraw because of AE or SAE, investigator should follow up the participant until the resolve of AE or SAE.
- Participants can require a complete withdraw from the study, all study behaviors could be stopped, including vaccination, biological specimen collection and safety observation. The data before withdrawal will not be used for analysis if he or she require so. If the participants allow the investigators use the data collected before the withdrawal, the data can be included in analysis.
- If a participant is infected by SARS-CoV-2 between day 0 and day 28 post-vaccination, immunogenicity data from he or she will not be included in analysis, but all SARS-CoV-2 infections occurred within 6 months after the vaccination should be documented and reported following the same procedure of SAE reporting, especial attention should be paid in case of the occurrence of antibody-dependent enhancement (ADE).
- Participants can require a partially withdraw from the study, such as refuse to vaccination or blood drawn only, but still participate in other procedures during the follow-up.

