9.6.2 Protocol deviation (including but not limited to)

- Beyond the visiting time window.
- Low compliance of participants, and the participants do not complete the blood sample collection.
- Serious adverse events do not report in time (SAE).
- Participants are treated with unallowed drugs (intramuscular, oral or intravenous corticosteroids for $\geq 2\text{mg/kg/days}$, continuous use for ≥ 14 days, or other immunosuppressants).
- The interval between vaccination with other vaccines is insufficient.
- Other reasons considered as protocol deviation by the principal investigator.

The protocol deviation should be recorded in detail. For the participants who exceeded the time window or had insufficient time interval of receiving other vaccines, the data of them can be included in the safety and immunogenicity analysis. For participants have other protocol deviation, the data of them can still be involved in the safety analysis, but can not be included in the immunogenicity analysis.

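### The exclusion list in Protocol 10.7.4 names no analysis set and contradicts the safety set and FAS in 10.7.3; separately, the deviation rule in 9.6.2 contradicts the FAS

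*Protocol*

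**What the plan says.** Section 10.7.3 defines the analysis sets.

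- **Safety set:** "All participants who received vaccination should be included in the safety evaluation", followed by "Data that violate the scheme should not be excluded".
- **FAS (primary for immunogenicity):** "FAS is based on ITT (intention to treat analysis) principle to determine the participants". Members must be eligible, be vaccinated and "have at least one blood testing result after vaccination". Nothing is required about correct dose or absence of deviations.
- **PPS (secondary):** a subset of the FAS without significant deviations or violations and with blood collected at every listed time point.

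Section 10.7.4 then lists exclusion criteria. They cover participants who did not meet the selection criteria, lacked follow-up data after vaccination or had seriously incomplete data. The list ends "Participants met the withdrawal criteria but did not withdraw; Participants received the wrong vaccination or incorrect dose". It names no analysis set. It follows a paragraph on both vaccine effect and safety, and comes directly before the safety and immunogenicity methods.

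Section 9.6.2 deals with protocol deviations. Data affected by visit-window or vaccine-interval deviations may be used in both the safety and immunogenicity analyses. With any other deviation the data may be used for safety, "but can not be included in the immunogenicity analysis". The listed deviations include incomplete blood collection, disallowed drugs and late SAE reporting ("Serious adverse events do not report in time (SAE").

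**The concern.** The primary endpoint is adverse reactions within 7 days, by dose group, with 36 participants per group. Section 10.3.2 builds all three doses from the same vial, using one, two or three vials, so a dosing error is a foreseeable event. Section 9.6.1 treats receipt of another group's vaccine as a violation and asks in particular for those participants' safety data. A list that then discards them takes informative records out of the primary analysis.

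On the immunogenicity side, a set built on the intention-to-treat principle would lose people with valid samples because one draw was missed or an SAE report was late. A late report is a failure of process and has no bearing on an antibody titre. Because the PPS already requires complete bleeds and no significant deviation, applying 9.6.2 to the FAS would largely erase the difference between the two sets that 10.7.3 wants compared.

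**Working it through.** The only stated figure involved is the sample size: 3 groups × 36 = 108, which reproduces. The rest is a comparison of rules, then an illustration of size.

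**Section 10.7.4 against 10.7.3, item by item, for a vaccinated participant**

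- *Wrong vaccine or incorrect dose:* in the safety set by 10.7.3, out by 10.7.4. If eligible with one post-vaccination blood result, also in the FAS by 10.7.3 and out by 10.7.4.
- *Met withdrawal criteria but stayed:* the same conflict with both sets.
- *Seriously incomplete data:* conflict with the safety set, and with the FAS when one blood result exists.
- *Did not meet selection criteria:* conflict with the safety set; none with the FAS, which requires eligibility anyway.
- *No follow-up data:* conflict with the safety set; none with the FAS when there is no post-vaccination blood result.

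**Section 9.6.2 against 10.7.3**

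- *Safety set:* no conflict, since 9.6.2 allows the data to be used for safety.
- *FAS:* an eligible participant with one missed draw, a disallowed drug or a late-reported SAE is in by 10.7.3 if one post-vaccination result exists, but out of all immunogenicity analysis by 9.6.2.
- Wrong vaccination is a violation under 9.6.1, so the wrong-dose exclusion comes from 10.7.4 alone.

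**Illustration for safety (assumed counts)**

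Suppose 6 of 36 in a group have an event: 6/36 = 16.7%. If 1, 2 or 3 of those six were misdosed and removed:

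- 5/35 = 14.3%
- 4/34 = 11.8%
- 3/33 = 9.1%

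Removing one misdosed person without the event gives 6/35 = 17.1%. Under the 10.7.3 rule nobody is dropped. This example treats all 36 as belonging to that group, so it shows the effect of removal and not that of regrouping by dose received.

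**Illustration for immunogenicity (assumed miss rates)**

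Table 8-3-1-2 has four post-vaccination humoral bleeds: day 14, day 28, month 3 and month 6. If a fraction m of participants misses each bleed independently, the share missing at least one is 1 − (1 − m)^4.

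- m = 1%: 1 − 0.99^4 = 3.9%; × 36 = 1.4
- m = 2%: 1 − 0.98^4 = 7.8%; × 36 = 2.8
- m = 5%: 1 − 0.95^4 = 18.5%; × 36 = 6.7

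Section 9.5.2 counts immunogenicity collection as complete once the bleeds up to day 28 are done. If 9.6.2 is read that way, only two bleeds count: at m = 5%, 1 − 0.95^2 = 9.8%; × 36 = 3.5.

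**The case against.** The strongest reply is that 10.7.3 has a rule specific to safety, that 9.6.1 and 9.6.2 point the same way, and that the 10.7.4 list reads like a per-protocol list whose label was lost. Sections 10.7.2 and 10.7.4 also refer to statistical analysis plans for detail. On this view an experienced analyst would let the safety rule govern, and the primary endpoint is in little danger. That is a fair forecast of what would probably happen, and it makes this a defect of scope and not a deliberate instruction to discard safety data. It does not remove the contradiction: whichever rule the analysis plan adopts, it departs from a protocol sentence. For the FAS there is no such safeguard, because 9.6.2 refers to the immunogenicity analysis without limiting this to the PPS.

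Three stronger readings are tempting but unsupported.

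- A reader might infer that 9.6.2 also shrinks the safety set. It says the opposite.
- A reader might infer that 10.7.4 drops people who left because of reactions. The item concerns people who met withdrawal criteria and stayed.
- A reader might add 9.4: "The data before withdrawal will not be used for analysis if he or she require so". That applies on the participant's own request after complete withdrawal, whatever the reason. It is a consent right, and a separate item in 9.4 requires follow-up of adverse events that led to withdrawal. It is not part of this point.

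The miss rates are also open to challenge. Participants stay in designated lodging for 14 days with daily visits (10.4.1), so a 5% miss rate at day 14 looks high. This is why a range is shown.

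**Conclusion.** The protocol is wrong as written on two counts. The unscoped 10.7.4 list contradicts the safety set for every item, and the FAS for wrong vaccine or dose, for meeting withdrawal criteria but staying, and for seriously incomplete data when a blood result exists. Section 9.6.2 contradicts the FAS only.

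The effect on safety cannot be sized from the protocol, since it depends on how many people are misdosed and whether they react. With 36 per group, one or two removals can move an incidence by a few percentage points. The effect of 9.6.2 runs from about 1 to about 7 of 36 per group for miss rates of 1% to 5% over four independent bleeds, and is about 3.5 of 36 at 5% if only two bleeds count. These are illustrations under assumed rates, not predictions; the 18.5% is the top of the range shown. The contradiction itself rests on no assumption.

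**What to change.** - In 10.7.4, state that the exclusion list applies to the PPS only and that the safety set follows 10.7.3. The PPS already excludes protocol violators, so this is consistent with its definition.
- State that safety is tabulated by dose actually received, and say how misdosed participants are grouped in the FAS.
- In 9.6.2, state that deviations do not remove anyone from the FAS, and that only deviations likely to alter the immune response remove a participant from the PPS. Delete late SAE reporting as a ground for exclusion from immunogenicity.
- Leave 9.4 unchanged for this purpose.

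The cost is protocol wording with matching text in the analysis plans. No new data, visits or participants are needed. It should be settled before the database is locked for the initial analysis, so that membership of each set is fixed before results are seen.
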